Appendix 2 Schedule of Activities (Open-Label Extension)

Week	Open-label Treatment Period																			Unplanned Visit ^a	Tx Completion ^b	Tx D/C ^b					
	77	81	85	89	93	97	101	105	109	113	117	121	125	129	133	137	141	145	149				153	157	161	165	169
Diagnostic classification			x			x			x			x			x			x			x			x			x ^c
MMSE ^d			x			x			x			x			x			x			x			x			x ^c
CDR ^d											x													x			x ^e
RBANS ^d											x													x			x ^e
ADAS-Cog 13 ^d											x													x			x ^e
Amsterdam iADL ^d											x													x			x ^e
ADCS-ADL ^d											x													x			x ^e
C-SSRS			x			x			x			x			x			x			x			x	x	x	x
CaGI-Alz ^z											x													x			x
Vital signs ^f	x	x	x	x	x	x	x	x	x	x	x	x	x	x	x	x	x	x	x	x	x	x	x	x	x	x	x ^g
Weight						x						x						x						x	x	x	x
Complete physical examination ^h						x						x						x						x			x
Limited physical examination ⁱ			x						x						x						x				x		
Neurological examination			x			x			x			x			x			x			x			x	x	x	x
MRI ^j				x																				x			x ^e
[¹⁸ F]GTP1 PET ^k																								x			x ^l
ECG																											x ^m
Hematology ⁿ												x													x	x	x
Chemistry and lipids ^o												x													x	x	x

Appendix 2 Schedule of Activities (Open-Label Extension) (cont.)

Week	Open-label Treatment Period																					Unplanned Visit ^a	Tx Completion ^b	Tx D/C ^b				
	77	81	85	89	93	97	101	105	109	113	117	121	125	129	133	137	141	145	149	153	157				161	165	169	
Coagulation ^p												x												x				
Pregnancy test ^q	x	x	x	x	x	x	x	x	x	x	x	x	x	x	x	x	x	x	x	x	x	x	x	x				
Urinalysis ^r												x													x	x	x	
Study drug administration	x	x	x	x	x	x	x	x	x	x	x	x	x	x	x	x	x	x	x	x	x	x	x	x				
Serum PK sample	x ^s				x ^t				x ^t				x ^t				x ^t				x ^t			x ^t		x ^e	x ^e	
Serum ADA sample ^u	x				x				x				x				x				x			x		x ^e	x ^e	
Blood sample for biomarkers ^v	x												x												x		x ^e	
LP for CSF sample for PK and biomarkers ^w																									x		x	
Concomitant medications ^x	x	x	x	x	x	x	x	x	x	x	x	x	x	x	x	x	x	x	x	x	x	x	x	x	x	x	x ^x	x ^x
Adverse events ^y	x	x	x	x	x	x	x	x	x	x	x	x	x	x	x	x	x	x	x	x	x	x	x	x	x	x	x ^y	x ^y

[¹⁸F]GTP1 = fluorine-18 Genentech tau probe 1; ADA=anti-drug antibody; ADAS-Cog=Alzheimer's Disease Assessment Scale–Cognitive Subscale; ADCS-ADL=Alzheimer's Disease Cooperative Study Group–Activities of Daily Living Inventory; CaGI-Alz = Caregiver Global Impression of Change Scales for Alzheimer's disease; C-SSRS=Columbia-Suicide Severity Rating Scale; CDR=Clinical Dementia Rating; COA=clinical outcome assessment; CSF=cerebrospinal fluid; D/C=discontinuation; eCRF=electronic Case Report Form; iADL=Instrumental Activity of Daily Living; LP=lumbar puncture; MMSE=Mini-Mental State Examination; MRI=magnetic resonance imaging; OLE=open-label extension; PET=positron emission tomography; PK=pharmacokinetic; RBANS=Repeatable Battery for the Assessment of Neuropsychological Status; Tx=treatment.

Notes: All postbaseline study visits must be scheduled in reference to the first dosing day (Week 1 visit). All activities/assessments in a given study visit must be performed within ±5 days of the scheduled visit, unless otherwise specified (e.g., [¹⁸F]GTP1 PET scans). On study drug administration visits that span multiple days, study drug administration must occur on the last day. On study drug administration days, all assessments must be performed prior to dosing, unless otherwise specified.

On study drug administration days, pre-infusion laboratory samples should be drawn 0–4 hours before the start of infusion, and post-infusion laboratory samples should be drawn 0–30 minutes after the end of infusion, unless otherwise specified.

Appendix 2

Schedule of Activities (Open-Label Extension) (cont.)

- ^a Visit not specified by the protocol. Assessments (possibly including PK sample collection) should be performed as clinically indicated.
- ^b Patients who complete the OLE treatment period will return to the clinic for a treatment completion visit (safety follow-up) at Week 181 (± 7 days). Patients who discontinue study drug prematurely in the OLE treatment period will return to the clinic for a treatment discontinuation visit 12 weeks (± 7 days) after the last dose of study drug.
- ^c Only perform assessment if discontinuation visit is ≥ 8 weeks after last assessment for this instrument.
- ^d Please see the GN39763 COA Manual for instructions on COA administration order, specification of list versions to use at each visit, rater roles, restrictions on raters, and additional details on COA administration and the endpoint reliability program. At all visits, all COA questionnaires/scales (excluding the diagnostic classification form) will be rater administered before the patient or rater or caregiver receives any information on disease status, prior to LP scheduled in the visit, and prior to the administration of study drug. In addition, on any given day when COAs are performed, all COAs (with the exception of the diagnostic classification form and the C-SSRS) must be completed prior to blood draws or imaging performed on the same day. For details on permitted concomitant medication use prior to COA assessments, see Section 4.1.2.
- ^e Only perform assessment if discontinuation visit is ≥ 16 weeks after last assessment for this instrument or procedure. However, if the patient discontinues study drug because of an infusion-related reaction, concurrent ADA and PK samples will also be collected at 12 weeks after the last administration of study drug.
- ^f Includes respiratory rate, pulse rate, and systolic and diastolic blood pressure while the patient is in a seated position, and temperature. Record abnormalities observed at baseline on the General Medical History and Baseline Conditions eCRF. At subsequent visits, record new or worsened clinically significant abnormalities on the Adverse Event eCRF. On study drug treatment visits, vital signs should be collected 0–4 hours prior to infusion and 60–90 minutes after completion of infusion.
- ^g Vital signs should be assessed on the same day(s) that the [^{18}F]GTP1 PET scan and/or LP are performed. Vital signs should be assessed just prior to injection of [^{18}F]GTP1 or initiation of the LP procedure, but no earlier than 1 hour prior to injection of [^{18}F]GTP1 or initiation of the LP procedure. Vital signs should also be assessed just after injection of [^{18}F]GTP1 or conclusion of the LP procedure, but no later than 1 hour after injection of [^{18}F]GTP1 or conclusion of the LP procedure.
- ^h Includes evaluation of the head, eyes, ears, nose, and throat, and the cardiovascular, dermatological, respiratory, and gastrointestinal systems. In addition, the musculoskeletal and genitourinary systems should be examined as clinically indicated. Record abnormalities observed at baseline on the General Medical History and Baseline Conditions eCRF. At subsequent visits, record new or worsened clinically significant abnormalities on the Adverse Event eCRF.
- ⁱ Perform a limited, symptom-directed examination at specified timepoints or as clinically indicated. Record new or worsened clinically significant abnormalities on the Adverse Event eCRF.

Appendix 2

Schedule of Activities (Open-Label Extension) (cont.)

- j* The MRI must be performed and assessed locally and in real time prior to any study drug dosing at the corresponding study visit. Study drug should be withheld if there are clinically significant new or clinically significant worsened MRI abnormalities identified in the local interpretation. However, if no such abnormalities are identified, the dose may be given prior to receipt of the central MRI report (see Section 5.1.1.2).
- k* If a [¹⁸F]GTP1 PET scan is performed at the baseline visit, [¹⁸F]GTP1 PET scans must be performed at all indicated postbaseline visits. [¹⁸F]GTP1 PET scans must be performed if [¹⁸F]GTP1 is available at the PET imaging center through the [¹⁸F]GTP1 distribution network, unless local restrictions preclude [¹⁸F]GTP1 PET imaging. If a [¹⁸F]GTP1 PET scan is not performed at the baseline visit, [¹⁸F]GTP1 PET scans become optional at any of the indicated postbaseline visits. Postbaseline [¹⁸F]GTP1 PET scans may be performed prior to or after study treatment administration at the corresponding visit. The Week 169 and treatment discontinuation visit [¹⁸F]GTP1 PET scan dates may be coordinated by the [¹⁸F]GTP1 distribution network on the basis of tracer availability and may be scheduled outside the ±14 day window around the scheduled visit should appropriate extenuating circumstances arise. If, at any time, local restrictions for radiation exposure disallow performing a [¹⁸F]GTP1 PET scan, the site should contact the Sponsor to discuss alternative timing.
- l* A [¹⁸F]GTP1 tau PET scan should only be performed if the following has been met: informed consent has been obtained, at least 24 weeks have elapsed since any previous [¹⁸F]GTP1 tau PET scan, and local annual radiation limits have not exceeded.
- m* Only perform assessment if clinically indicated.
- n* Hematology includes WBC count, RBC count, hemoglobin, hematocrit, platelet count, differential count (absolute counts of neutrophils, eosinophils, basophils, monocytes, lymphocytes, other cells).
- o* Chemistry panel (serum or plasma) includes sodium, potassium, chloride, magnesium, bicarbonate, glucose, BUN or urea, creatinine, total protein, albumin, phosphorus, calcium, total and direct bilirubin, alkaline phosphatase, ALT, AST, uric acid, LDH, gamma glutamyl transpeptidase, lactate dehydrogenase, creatine kinase. Glomerular filtration rate should also be calculated from creatinine using the Cockcroft-Gault formula. Lipid panel includes cholesterol, LDL cholesterol, HDL cholesterol, triglycerides.
- p* Coagulation panel includes INR, aPTT, and PT; the coagulation panel should be measured within 90 days prior to any LP or within an interval consistent with the local standard of care, whichever is shorter. If required per local standard of care, additional coagulation panel tests may be performed at central laboratory or at a local laboratory. For patients taking multiple anti-platelet medications, the investigator should determine (per local standards of care) whether the temporary discontinuation of one or more anti-platelet medications prior to LP is warranted (e.g., continuing aspirin and discontinuing thienopyridine derivatives for 1–2 weeks prior to LP). The Week 169 coagulation laboratory tests are only applicable to patients participating in the optional CSF collection (lumbar puncture).
- q* For women of childbearing potential, urine pregnancy tests will be performed at specified subsequent visits, prior to dosing. If a urine pregnancy test is positive, it must be confirmed by a serum pregnancy test. Pregnancy tests must be negative prior to dosing with MTAU9937A (or placebo) or [¹⁸F]GTP1 or an amyloid radioligand.

Appendix 2

Schedule of Activities (Open-Label Extension) (cont.)

- r Includes dipstick (pH, specific gravity, glucose, protein, ketones, blood). Microscopic examination (sediment, RBCs, WBCs, casts, crystals, epithelial cells, bacteria) should be performed if the dipstick is abnormal.
- s Serum PK samples should be taken 0–4 hours before the start of infusion and 1 hour (\pm 15 minutes), 2 hours \pm 20 minutes), and 4 hours (\pm 30 minutes) after the end of infusion.
- t Serum PK samples should be taken 0–4 hours before the start of infusion and 0–30 minutes after the end of infusion.
- u At all indicated visits, serum ADA sample should be taken 0–4 hours before the start of infusion. In addition, concurrent ADA and PK samples should also be collected in patients with signs and symptoms of an infusion-related reaction at the time of the infusion-related event, for analyses of antibodies to MTAU9937A and/or other components of the drug product. Concurrent ADA and PK samples should also be collected in all patients at the treatment completion or treatment discontinuation visit (see footnote e, above, for more details).
- v Blood biomarker samples should be taken 0–4 hours before the start of infusion.
- w LPs are optional during the OLE period.
- x Medication (e.g., prescription drugs, over-the-counter drugs, vaccines, herbal or homeopathic remedies, nutritional supplements) used by a patient in addition to protocol-mandated treatment until the final study visit.
- y All adverse events will be reported until 12 weeks after the last dose of study drug. After this period, all deaths, regardless of cause, should be reported. In addition, the Sponsor should be notified if the investigator becomes aware of any serious adverse event that is believed to be related to prior study drug or [18 F]GTP1 or amyloid radioligand treatment (see Section 5.6). The investigator should follow each adverse event until the event has resolved to baseline grade or better, the event is assessed as stable by the investigator, the patient is lost to follow-up, or the patient withdraws consent. Every effort should be made to follow all serious adverse events considered to be related to study drug or [18 F]GTP1 or amyloid radioligand or trial-related procedures until a final outcome can be reported.
- z Both CaGI-Alz assessments referring to changes relative to start of study and relative to the prior assessment (*e.g., the prior 6 months*) should be administered.

Appendix 3

National Institute on Aging/Alzheimer’s Association Criteria for Mild Alzheimer’s Disease

NIA-AA category	Description

Probable Dementia: core Clinical Criteria Meets criteria for dementia described earlier in the text, and in addition, has the following characteristics:
	
A. Insidious onset. Symptoms have a gradual onset over months to years, not sudden over hours or days;
 
B. Clear-cut history of worsening of cognition by report or observation; and
 
C. The initial and most prominent cognitive deficits are evident on history and examination in one of the following categories.
 
a. Amnestic presentation: It is the most common syndromic presentation of AD dementia. The deficits should include impairment in learning and recall of recently learned information. There should also be evidence of cognitive dysfunction in at least one other cognitive domain, as defined earlier in the text.
 
b. Non-amnestic presentations:
 
Language presentation: The most prominent deficits are in word-finding, but deficits in other cognitive domains should be present.
 
Visuospatial presentation: The most prominent deficits are in spatial cognition, including object agnosia, impaired face recognition, simultanagnosia, and alexia. Deficits in other cognitive domains should be present.
 
Executive dysfunction: The most prominent deficits are impaired reasoning, judgment, and problem solving. Deficits in other cognitive domains should be present.
 
D. The diagnosis of probable AD dementia should not be applied when there is evidence of (a) substantial concomitant cerebrovascular disease, defined by a history of a stroke temporally related to the onset or worsening of cognitive impairment; or the presence of multiple or extensive infarcts or severe white matter hyperintensity burden; or (b) core features of Dementia with Lewy bodies other than dementia itself; or (c) prominent features of behavioral variant frontotemporal dementia; or (d) prominent features of semantic variant primary progressive aphasia or nonfluent/agrammatic variant primary progressive aphasia; or (e) evidence for another concurrent, active neurological disease, or a non-neurological medical comorbidity or use of medication that could have a substantial effect on cognition.

Appendix 3

National Institute on Aging/Alzheimer's Association Criteria for Mild Alzheimer's Disease (cont.)

NIA-AA category	Description
Probable AD dementia with increased level of certainty	
Probable AD dementia with documented decline
 
In persons who meet the core clinical criteria for probable AD dementia, documented cognitive decline increases the certainty that the condition represents an active, evolving pathologic process, but it does not specifically increase the certainty that the process is that of AD pathophysiology.
 
Probable AD dementia with documented decline is defined as follows: evidence of progressive cognitive decline on subsequent evaluations based on information from informants and cognitive testing in the context of either formal neuropsychological evaluation or standardized mental status examinations.
 
Probable AD dementia in a carrier of a causative AD genetic mutation
 
In persons who meet the core clinical criteria for probable AD dementia, evidence of a causative genetic mutation (in APP, PSEN1, or PSEN2), increases the certainty that the condition is caused by AD pathology. The workgroup noted that carriage of the $\epsilon 4$ allele of the apolipoprotein E gene was not sufficiently specific to be considered in this category.

Probable AD dementia with evidence of the AD pathophysiological process	
AD dementia is part of a continuum of clinical and biological phenomena. AD dementia is fundamentally a clinical diagnosis. To make a diagnosis of AD dementia with biomarker support, the core clinical diagnosis of AD dementia must first be satisfied.
 
Relevant biomarkers include amyloid-β(CSF or PET); tau (CSF or PET)

AD=Alzheimer's disease; CSF=cerebrospinal fluid; NIA-AA=National Institute on Aging/Alzheimer's Association; PET=positron emission tomography.

Reference: McKhann GM, Knopman DS, Chertkow H, et al. The diagnosis of dementia due to Alzheimer's disease: recommendations from the National Institute on Aging-Alzheimer's Association workgroups on diagnostic guidelines for Alzheimer's disease. *Alzheimers Dement* 2011;7:263–9.

Appendix 4
National Institute on Aging/Alzheimer’s Association Criteria for
Prodromal Alzheimer’s Disease (Mild Cognitive Impairment due
to Alzheimer’s Disease)

NIA-AA category	Clinical and Cognitive Criteria
Clinical Criteria	Cognitive concern reflecting a change in cognition reported by patient or informant or clinician (i.e., historical or observed evidence of decline over time) Objective evidence of Impairment in one or more cognitive domains, typically including memory (i.e., formal or bedside testing to establish level of cognitive function in multiple domains) Preservation of independence in functional abilities Not demented
Etiology of MCI consistent with AD pathophysiological process	Rule out vascular, traumatic, medical causes of cognitive decline, where possible. Provide evidence of longitudinal decline in cognition, when feasible Report history consistent with AD genetic factors, where relevant
pAD dementia with evidence of the AD pathophysiological process	pAD is part of a continuum of clinical and biological phenomena. pAD is fundamentally a clinical diagnosis. To make a diagnosis of pAD with biomarker support, the core clinical diagnosis of pAD must first be satisfied. Relevant biomarkers include amyloid-β(CSF or PET); tau (CSF or PET)

AD=Alzheimer’s disease; CSF=cerebrospinal fluid; MCI=mild cognitive impairment; NIA-AA=National Institute on Aging/Alzheimer’s Association; pAD=prodromal AD; PET=positron emission tomography.

Reference: Albert MS, DeKosky ST, Dickson B, et al. The diagnosis of mild cognitive impairment due to Alzheimer’s disease: recommendations from the National Institute on Aging-Alzheimer’s Association workgroups on diagnostic guidelines for Alzheimer’s disease. *Alzheimers Dement* 2011;7:270–79.

Appendix 5 Anaphylaxis Precautions

The following equipment is needed in the event of a suspected anaphylactic reaction during study drug infusion:

- Monitoring devices: ECG monitor, blood pressure monitor, oxygen saturation monitor, and thermometer
- Oxygen
- Epinephrine for intravenous, intramuscular, and endotracheal administration in accordance with institutional guidelines
- Antihistamines
- Corticosteroids
- Intravenous infusion solutions, tubing, catheters, and tape

The following are the procedures to follow in the event of a suspected anaphylactic reaction during study drug infusion:

- Stop the study drug infusion.
- Call for additional medical assistance.
- Maintain an adequate airway.
- Ensure that appropriate monitoring is in place, with continuous ECG and pulse oximetry monitoring, if possible.
- Administer antihistamines, epinephrine, or other medications as required by participant status and as directed by the physician in charge.
- Continue to observe the participant and document observations.
- Draw serum samples for immunogenicity testing.
- Ask participant to return for washout immunogenicity sample (12 weeks after last dose) if appropriate.

Appendix 6 World Health Organization Toxicity Grading Scale

Appendix: WHO TOXICITY GRADING SCALE FOR DETERMINING THE SEVERITY OF ADVERSE EVENTS

HEMATOLOGY				
ITEM	Grade 1 Toxicity	Grade 2 Toxicity	Grade 3 Toxicity	Grade 4 Toxicity
Hemoglobin	9.5 - 10.5 gm/dl	8.0 - 9.4 gm/dl	6.5 - 7.9 gm/dl	< 6.5 gm/dl
Absolute Neutrophil Count	1000-1500/mm ³	750-999/mm ³	500-749/mm ³	500-749/mm ³
Platelets	75000-99000/mm ³	50000-74999/mm ³	20000-49000/mm ³	<20000/mm ³
Prothrombin Time (PT)	1.01 - 1.25 x ULN	1.26-1.5 x ULN	1.51 -3.0 x ULN	>3 x ULN
Activated Partial Thromboplastin (APPT)	1.01 -1.66 x ULN	1.67 - 2.33 x ULN	2.34 - 3 x ULN	3 x ULN
Fibrinogen	0.75 - 0.99 X LLN	0.50 - 0.74 x LLN	0.25 - 0.49 x LLN	< 0.25 x LLN
Fibrin Spilt Product	20-40 mcg/ml	41-50 mcg/ml	51-60 mcg/ml	> 60 mcg/ml
Methemoglobin	5 - 9.9 %	10.0 - 14.9 %	15.0 - 19.9%	> 20 %
LIVER ENZYMES				
AST (SGOT)	1.25 - 2.5 x ULN	2.6 - 5 x ULN	5.1 - 10 x ULN	10 x ULN
ALT (SGPT)	1.25 - 2.5 x ULN	2.6 - 5 x ULN	5.1 - 10 x ULN	10 x ULN
GGT	1.25 - 2.5 x ULN	2.6 - 5 x ULN	5.1 - 10 x ULN	10 x ULN
Alkaline Phosphatase	1.25 - 2.5 x ULN	2.6 - 5 x ULN	5.1 - 10 x ULN	10 x ULN
Amylase	1.1 - 1.5 x ULN	1.6 - 2.0 x ULN	2.1 - 5.0 x ULN	> 5.1 x ULN
CHEMISTRIES				
Hyponatremia	130-135 mEq/L	123-129 mEq/L	116-122 mEq/L	< 116 or mental status changes or seizures
Hypernatremia	146-150 mEq/L	151-157 mEq/L	158-165 mEq/L	> 165 mEq/L or mental status changes or seizures
Hypokalemia	3.0 - 3.4 mEq/L	2.5 - 2.9 mEq/L	2.0 - 2.4 mEq/L or intensive replacement Rx required or hospitalization required	< 2.0 mEq/L or paresis or ileus or life-threatening arrhythmia
Hyperkalemia	5.6 - 6.0 mEq/L	6.1 - 6.5 mEq/L	6.6 - 7.0 mEq/l	> 7.0 mEq/L or life-threatening arrhythmia
Hypoglycemia	55-64 mg/dL	40-54 mg/dL	30-39 mg/dL	<30 mg/dL or mental status changes or coma

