TEST PRODUCTS: MTAU9937A (RO7105705) and [¹⁸F]GTP1 (RO6880276)

MEDICAL MONITOR: [REDACTED], M.D., Ph.D.

SPONSOR: Genentech, Inc.

I agree to conduct the study in accordance with the current protocol.

Principal Investigator's Name (print)

Principal Investigator's Signature

Date

Please retain the signed original of this form for your study files. Please return a copy of the signed form as instructed by your Contract Research Associate.

PROTOCOL SYNOPSIS

TITLE: A PHASE II, MULTICENTER, RANDOMIZED, DOUBLE-BLIND, PLACEBO-CONTROLLED, PARALLEL-GROUP, EFFICACY, AND SAFETY STUDY OF MTAU9937A IN PATIENTS WITH PRODROMAL TO MILD ALZHEIMER'S DISEASE

PROTOCOL NUMBER: GN39763

VERSION NUMBER: 4

EUDRACT NUMBER: 2017-001800-31

IND NUMBERS: 129270, 125702

TEST PRODUCTS: MTAU9937A (RO7105705) and [¹⁸F]GTP1 (RO6880276)

PHASE: Phase II

INDICATION: Alzheimer's Disease

SPONSOR: Genentech, Inc.

Objectives and Endpoints

This study will evaluate the efficacy, safety, pharmacokinetics, and pharmacodynamics of MTAU9937A in patients with prodromal or mild Alzheimer's disease (AD), ages 50–80, who are amyloid positive by cerebrospinal fluid (CSF) or amyloid positron emission tomography (PET). Specific objectives and corresponding endpoints for the study are outlined below.

Primary	
Efficacy Objective	Corresponding Endpoints

To evaluate the efficacy of MTAU9937A compared with placebo	
Change from baseline to Week 73 on the CDR-SB
Safety Objective	Corresponding Endpoints

To evaluate the safety and tolerability of MTAU9937A compared with placebo	
Nature, frequency, severity, and timing of adverse events and serious adverse events. Severity of adverse events will be determined through use of the WHO toxicity grading scale.Changes from baseline in vital signs, physical findings, neurologic findings, ECG, and clinical laboratory results during and following MTAU9937A administrationChanges from baseline in suicidal ideation and behavior during and following MTAU9937A administration as assessed by the C-SSRSNature, frequency, severity, and timing of neuroimaging abnormalities

Secondary	
Efficacy Objective	Corresponding Endpoints

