5.2.2 Serious Adverse Events (Immediately Reportable to the Sponsor)

A serious adverse event is any adverse event that meets any of the following criteria:

- Is fatal (i.e., the adverse event actually causes or leads to death)
- Is life threatening (i.e., the adverse event, in the view of the investigator, places the patient at immediate risk of death)

This does not include any adverse event that, had it occurred in a more severe form or was allowed to continue, might have caused death.

- Requires or prolongs inpatient hospitalization (see Section 5.3.5.11)

- Results in persistent or significant disability/incapacity (i.e., the adverse event results in substantial disruption of the patient's ability to conduct normal life functions)
- Is a congenital anomaly/birth defect in a neonate/infant born to a mother exposed to study drug or [¹⁸F]GTP1 or an amyloid radioligand (if considered to be an IMP)
- Is a significant medical event in the investigator's judgment (e.g., may jeopardize the patient or may require medical/surgical intervention to prevent one of the outcomes listed above)

The terms "severe" and "serious" are not synonymous. Severity refers to the intensity of an adverse event (e.g., rated as mild, moderate, or severe, or according to National Cancer Institute Common Terminology Criteria for Adverse Events; see Section 5.3.3); the event itself may be of relatively minor medical significance (such as severe headache without any further findings).

Severity and seriousness need to be independently assessed for each adverse event recorded on the eCRF.

Serious adverse events are required to be reported by the investigator to the Sponsor immediately (i.e., no more than 24 hours after learning of the event; see Section 5.4.2 for reporting instructions).

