5.3.3 Assessment of Severity of Adverse Events

The WHO toxicity grading scale (see Appendix 6) will be used for assessing adverse event severity. Table 5 will be used for assessing severity for adverse events that are not specifically listed in the WHO toxicity grading scale.

Table 5 Adverse Event Severity Grading Scale for Events Not Specifically Listed in WHO Toxicity Grading Scale

Grade	Severity
1	Mild; transient or mild discomfort (<48 hours); no medical intervention or therapy require
2	Moderate; mild to moderate limitation in activity; some assistance may be needed; no or minimal medical intervention or therapy required
3	Severe; marked limitation in activity; some assistance usually required; medical intervention or therapy required; hospitalization possible
4	Life-threatening; extreme limitation in activity; significant assistance required; significant medical intervention or therapy required, hospitalization or hospice care probable

Notes: Developed by the Division of Microbiology and Infectious Diseases.

Regardless of severity, some events may also meet seriousness criteria. Refer to definition of a serious adverse event (see Section 5.2.2).

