Appendix 6 World Health Organization Toxicity Grading Scale (cont.)

**Appendix: WHO TOXICITY GRADING SCALE FOR DETERMINING
THE SEVERITY OF ADVERSE EVENTS**

OTHER PARAMETERS				
Fever: oral, > 12 hours	37.7 - 38.5 C or 100.0 - 101.5 F	38.6 - 39.5 C or 101.6 - 102.9 F	39.6 - 40.5 C or 103 - 105 F	> 40 C or > 105 F
Headache	mild, no Rx therapy	transient, moderate; Rx required	severe; responds to initial narcotic therapy	intractable; required repeated narcotic therapy
Fatigue	no decrease in ADL	normal activity decreased 25- 50%	normal activity decreased > 50% can't work	unable to care for self
Allergic Reaction	pruritus without rash	localized urticaria	generalized urticaria; angioedema	anaphylaxis
Local Reaction	tenderness or erythema	induration < 10 cm or phlebitis or inflammation	induration > 10 cm or ulceration	necrosis
Mucocutaneous	erythema; pruritus	diffuse, maculo papular rash, dry desquamation	vesiculation, moist desquamation, or ulceration	exfoliative dermatitis, mucous membrane involvement or erythema, multiforme or suspected Stevens- Johnson or necrosis requiring surgery

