4.5 SAFETY ANALYSES

The safety analysis population will consist of all randomized patients who received at least one dose of either MTAU9937A or placebo, or GTP1, with patients grouped according to treatment arm. Patients will be analyzed according to actual MTAU9937A treatment received.

All adverse events that occur after informed consent is given will be summarized by MedDRA mapped term, appropriate thesaurus level, and toxicity grade. In addition, all serious adverse events, including deaths and events leading to discontinuation, will be listed separately and summarized.

Laboratory data will be summarized by descriptive statistics by treatment group. In addition, all laboratory abnormalities will be summarized by grade using the WHO grading scale.

Dose-limiting adverse events and adverse events of special interest will be listed and summarized by treatment group.

Vital signs (pulse rate, blood pressure, body temperature, and respiratory rate), weight, and other disease-specific data will be summarized by descriptive statistics by treatment group. Changes from baseline will be summarized by treatment group.

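### Two rows of the Appendix 6 severity scale are internally inconsistent: neutrophil Grades 3 and 4 are the same band, and the fever limits disagree between Celsius and Fahrenheit (minor)

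*Protocol*

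**What the plan says.** The protocol's objectives table (Synopsis and Section 2) places adverse event severity under the primary safety objective: "Severity of adverse events will be determined through use of the WHO toxicity grading scale". SAP Section 2.1.3 lists the same endpoint. Protocol Section 5.3.3 sends the investigator to Appendix 6 for the scale and keeps Table 5 for "adverse events that are not specifically listed in the WHO toxicity grading scale". For laboratory data, SAP Section 4.5 states that "all laboratory abnormalities will be summarized by grade using the WHO grading scale", as does protocol Section 6.5. The SAP prints no bands of its own and gives no rule for a value that meets two grades or none.

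Two rows of Appendix 6 matter here:

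- **Absolute neutrophil count (Hematology).** The Grade 3 and Grade 4 cells read "500-749/mm ³ 500-749/mm ³".
- **Fever (Other Parameters; oral, lasting more than 12 hours).** Grade 3 is "39.6 - 40.5 C or 103 - 105 F". Grade 4 is anything above 40 C or above 105 F.

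**The concern.** A grading scale has to give each value one grade. If the bands overlap, whoever applies the table must choose between two grades. If a band is missing, a value gets no grade.

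For neutrophils the missing band is the lowest, so the most severe counts have no printed grade. For fever, the grade can depend on the unit in which the temperature is recorded. The trial ran in North America, Europe and the Asia-Pacific region, and the vital signs section (protocol Section 4.5.6) states no temperature unit. The same fever could therefore be graded differently at two sites.

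What is at stake is the reproducibility of a descriptive safety output. A programmer or investigator would have to adopt a rule that neither document records.

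**Working it through.** The plan states no figure to reproduce. The check applies the printed bands literally and lists every grade that a value meets. All bands come from Appendix 6.

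**1. Neutrophils (/mm³).** Grade 1 is 1000–1500, Grade 2 is 750–999, Grade 3 is 500–749 and Grade 4 is 500–749.

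| Count | Grades met |
|---|---|
| 0, 100, 300, 499 | none |
| 500, 600, 749 | 3 and 4 |
| 750, 999 | 2 |
| 1000, 1500 | 1 |

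Other rows for falling values have an open-ended Grade 4:

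- Hemoglobin: Grade 3 is 6.5–7.9 and Grade 4 is below 6.5 gm/dl.
- Platelets: Grade 3 is 20000–49000 and Grade 4 is below 20000/mm³.
- Fibrinogen: Grade 3 is 0.25–0.49 and Grade 4 is below 0.25 times the lower limit of normal.

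Only the neutrophil row repeats the Grade 3 band.

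**2. Fever.** The conversion is F = 1.8 × C + 32. The Celsius bands are Grade 2 38.6–39.5, Grade 3 39.6–40.5 and Grade 4 above 40. The Fahrenheit bands are Grade 2 101.6–102.9, Grade 3 103–105 and Grade 4 above 105.

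| C | Grade in C | F = 1.8C + 32 | Grade in F |
|---|---|---|---|
| 39.5 | 2 | 103.1 | 3 |
| 39.6 | 3 | 103.3 | 3 |
| 40.0 | 3 | 104.0 | 3 |
| 40.1 | 3 and 4 | 104.2 | 3 |
| 40.5 | 3 and 4 | 104.9 | 3 |
| 40.6 | 4 | 105.1 | 4 |

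The Grade 4 limits are 40 C = 104.0 F and 105 F = (105 − 32)/1.8 = 40.56 C. They differ by 0.56 C, or 1 F. The Grade 3/4 overlap exists only in Celsius; in Fahrenheit the two grades meet at 105 without overlap.

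**3. Can another provision resolve it?** Table 5 cannot, because it covers only events missing from the WHO scale, and both neutrophils and fever are listed. The SAP adds nothing.

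**4. Effect on a Grade 3-or-higher count.** The Grade 3/4 overlaps leave it unchanged. The missing neutrophil band would lower it, because counts below 500/mm³ carry no grade. The 39.5 C mismatch could move a fever across the Grade 2/3 line.

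**The case against.** The strongest objection is that the neutrophil item rests on one table cell read from a PDF. The same appendix has Grade 4 cells with no greater-than sign (APTT, AST, ALT, GGT, alkaline phosphatase), which may have been lost in reading; nothing here relies on them. Losing a symbol is easier to explain than repeating a full cell, so the item stands, subject to a check of the source. The fever row reads as intact and does not depend on that check.

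The consequence is also small. The laboratory endpoint under the primary safety objective is change from baseline, not grade. Laboratory data also get descriptive summaries, and serious events and events of special interest are listed separately. The special-interest category defined by grade is infusion-related reactions of Grade 3 or higher (protocol Section 5.2.3), which a Grade 3/4 overlap cannot alter. I found no rule triggered by a neutrophil or fever grade. All of this stands, and it limits the point to a minor one.

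Three stronger readings are tempting, and the documents do not support them:

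- **That the worst values in general go ungraded.** This is true only of neutrophils below 500/mm³. Fever of 40.6 C or more is Grade 4 in both units.
- **That severe neutrophil counts would be lost.** Differential counts are measured centrally as numbers (protocol Section 4.5.9), so the values remain. No grading program is specified, so how one would treat the gap is not known.
- **That the protocol prescribes two rival severity scales.** Section 5.2.2 does contain the words "according to National Cancer Institute Common Terminology Criteria for Adverse Events; see Section 5.3.3", but they belong to a parenthetical example explaining that severe and serious mean different things. The operative text is consistent: the WHO scale, with Table 5 for unlisted events.

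**Conclusion.** The point holds as a minor internal inconsistency in two rows of an operative table. As printed, neutrophil counts of 500–749/mm³ meet two grades and counts below 500/mm³ meet none. Temperatures above 40.0 and up to 40.5 C meet two grades in Celsius and one in Fahrenheit, and 39.5 C changes grade with the unit.

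The neutrophil part assumes that the repeated cell is in the source document. The fever part matters in practice only if sites record or grade in different units, or if Celsius sites choose differently within the overlap; the documents do not show whether either happened. They also give no expected frequency for such values. That few patients would be affected is a judgement, not a calculation. Efficacy results are untouched, and the documents do not support a conclusion that the primary safety assessment as a whole is compromised.

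**What to change.** 1. Check the neutrophil Grade 4 cell against the source PDF and the scale from which it was copied.
2. Reconcile the neutrophil and fever rows so that the bands are mutually exclusive and exhaustive and the Celsius and Fahrenheit limits agree at every grade boundary. The choice of limits is for the sponsor; none is proposed here.
3. Record the reconciled bands in the SAP, or in a specification that it cites, so that the Section 4.5 grading programs use them.
4. Re-derive neutrophil grades from the stored central laboratory values.
5. Review fever events whose recorded temperature falls in the affected ranges. Their severity was assigned by investigators, and the row also requires more than 12 hours' duration, so a single vital-sign reading may not be enough to regrade them.

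The cost is a correction to two table rows, a short SAP entry and a rerun of the grade tables. No new data are needed for the laboratory part. The fever part may need a few site queries if the temperature was not captured with the event.
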